## **4.2.5 Extent of Exposures**

### **4.2.5.1 Study Therapy**

Extent of exposure is defined as the number of days between the start and the end dates of study therapy, where the start date of study therapy is the date of the first dose of investigative or comparator treatment, and the end date of study therapy is the last known dose of investigative or comparator treatment during the double-blind randomized treatment period, ie,

Extent of exposure=Last dosing date - First dosing date + 1.

Extent of exposure to the investigational product will be summarized using Safety analysis set for the double-blind treatment period regardless of rescue and prior to rescue respectively, presenting the numbers and percents of patients with an extent of exposure within the following day ranges by treatment group: 1 to 14, 15 to 28, 29 to 42, 43 to 56, 57 to 84, 85 to 112, 113 to 168, and  $\geq 169$  days. Also the mean, SD, median and range of extent of exposure to study medication will be presented by treatment group.

Extent of exposure for the investigational product during the double-blind treatment period will be summarized and listed by patient. Additionally, a listing of randomization scheme and a listing of patients by batch number of investigational product will be produced.

Also, rescue medication usage (number of patients taking rescue medication or insulin) will be summarized by treatment group based on CRF records. A by patient listing for rescue medication usage will be presented for all rescued patients during double-blind treatment period.

#### 4.2.5.2 Treatment Compliance

Percent treatment compliance is calculated during the double-blind treatment period for the blinded study medication. Percent compliance is defined as the number of tablets taken, divided by the number of tablets that should have been taken. A patient is considered compliant if percent compliance is between 80% and 120%, inclusive. The number of tablets that should have been taken is calculated as (date of the last investigational dose - date of 1st investigational dose during randomized treatment period + 1), times the prescribed daily dose. Total number of tablets taken is the difference between total number of tablets dispensed minus total number of tablets returned over the entire randomized treatment period. All dates and tablets counts data are to be taken from the “Drug Accountability” or DA module in CRF.

The number and percent of patients compliant with double-blind study drug during the double-blind treatment period will be summarized for the safety analysis set.

#### 4.2.6 Efficacy Variables

##### 4.2.6.1 Primary Efficacy Variable

The primary objective of this study is to compare the mean change from baseline in HbA1c between dapagliflozin 10 mg and placebo, after 24 weeks of oral administration of double-blind treatment in patients with type 2 diabetes and CKD stage 3A. The primary estimand will be the treatment difference at Week 24 if all patients had remained in the trial and received treatment as planned without rescue medication. The analysis of the primary estimand will include all available data up to Week 24 or premature discontinuation of randomized treatment, whichever occurs first.

The null and alternative hypotheses of interest are:

$$H_0: \mu_s = \mu_p \text{ VS } H_a: \mu_s \neq \mu_p,$$

Where  $\mu_s$  and  $\mu_p$  are mean change from baseline to week 24 in HbA1c for study medication dapagliflozin and placebo groups respectively.

For rescued patients, measurements obtained after rescued medication or rescued insulin will be excluded. For patients discontinuing double-blind medication, measurements obtained after discontinuation will be excluded.

The primary analysis for the change in HbA1c from baseline at Week 24 will be based on longitudinal repeated measures analysis as described in Section 4.1.6.1. For all patients that are administered rescue therapy or discontinue treatment during the double-blind treatment period, only those measurements made on or prior to rescue or treatment discontinuation, (whichever occurs first) the will be included in analysis. For the primary efficacy analysis, the additional 3-way interaction term Baseline\*Week\*Treatment will be used as a model check to assess if there is statistically significant treatment effect across visits which differs in dependency on baseline values.

Point estimates and 95% confidence intervals for the mean change within each treatment group as well as for the differences in mean change between dapagliflozin 10 mg treatment group and the placebo treatment group will be calculated. P-value will be calculated to compare the treatment effect in the dapagliflozin 10 mg treatment group to that in the placebo treatment group.

#### 4.2.6.2 Sensitivity Analysis

To assess the robustness of the primary efficacy analysis, and to compare the results with previous studies, the sensitivity analyses on the primary efficacy endpoints will be carried out using the following approaches:

- Repeat of the primary analyses for the Per Protocol Set (if warranted) which is a subset of the Full Analysis Set and will consist of patients who do not deviate from the terms of the protocol, utilizing the longitudinal repeated measures methodology described in Section 4.1.6.1, only include measurements prior to rescue and treatment discontinuation.

Note the sensitivity analysis using the Per Protocol Set will be applied to primary efficacy endpoints only if there the Per Protocol Set has a minimum of 10% fewer patients for any treatment group than the Full Analysis Set.

- Repeat of the primary analyses for the Full Analysis Set who have a baseline assessment and any post-baseline double-blind treatment period HbA1c assessment utilizing longitudinal repeated measures methodology described in Section 4.1.6.1, with adjustment for baseline eGFR and baseline eGFR-by-week interaction, in addition to adjustment for baseline HbA1c and baseline HbA1c-by-week interaction, only include measurements prior to rescue and treatment discontinuation.
- Repeat of the primary analyses for the Randomized Set who have a baseline assessment regardless of rescue or treatment discontinuation utilizing ANCOVA at Week 24 within the framework of MI-RD imputation described in Section 4.1.7.3.
- Repeat of the primary analyses for the Randomized Set who have a baseline assessment regardless of rescue or treatment discontinuation utilizing ANCOVA at Week 24 within the framework of Washout-imputation described in Section 4.1.7.4.

Summaries and analyses supporting the primary efficacy objective are:

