Notably, dapagliflozin's ability to inhibit renal glucose reabsorption declines with decreasing eGFR. Urinary glucose excretion is about 50% lower in patients with T2DM treated with dapagliflozin having CKD stage 3, as compared with patients with normal or mildly impaired renal function. Such eGFR dependence is expected given the fall in filtered glucose load with worsening CKD stage. In a previous study, dapagliflozin did not have a significant impact on glycemic control in patients with more advanced CKD, although there was a modest decrease in HbA1c and FPG in patients with a GFR of 45–59 ml/min (Kohan et al 2014). However, that study suffered from several limitations. The use of insulin-based regimens in almost two-thirds of patients, often with sliding scale administration, made accurate capture of insulin dosing difficult. Unmeasured differential behaviour with respect to sliding scale and other adjustments of insulin between placebo and dapagliflozin could have blunted the apparent efficacy of dapagliflozin. A second limitation was the relatively small size of the study, which was powered for a 0.6% change in HbA1c, and therefore limited in its ability to demonstrate smaller glycemic effects and thus, the study may be considered underpowered and subject to type 2 error. Other factors such as a very short placebo lead-in period and a relatively large placebo effect in this study could potentially also have affected and obscured the interpretation of the data. In other clinical studies, which did not suffer from the limitations described above, SGLT2-inhibitors have been shown to be safe and effective in T2DM patients with moderate renal impairment lending support to further studies in this specific patient segment (Yale et al 2013, Barnett et al 2014).

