- ^e Randomized patients discontinuing study medication or requiring rescue should have Week 24 procedures done at the time of anti-diabetic rescue or study medication discontinuation. All patients who discontinue study medication will be asked to continue ordinary visit schedule, unless they entirely withdraw consent from the study. In patients discontinuing the study due to AE/SAE, the Investigator will follow the patients until the event has resolved or stabilized.
- ^f The signature of the ICF by the prospective patient should be obtained at Visit 1. When only the Informed Consent is signed, and all other screening visit procedures are completed.
- ^g eGFR value for inclusion is based on eGFR value between 45 – 59 mL/minute/1.73 m² at Visit 1, or Visit 2, or Visit 3.
- ^h Lab values for inclusion will be based on results from Visit 2 and Visit 3. Lab values from Visit 4 will be used as baseline values for study entry.
- ⁱ A brief physical examination should include cardiovascular (CV), lungs, abdomen, and extremities; and any organ systems pertinent to the patient's signs, symptoms, or AEs.
- ^j A complete physical examination should include general appearance, head, eyes, ears, nose, throat, neck, CV, lungs, abdomen, lymph nodes, extremities, neurological, skin, and musculoskeletal.
- ^k The 12-lead ECG must be performed at Visit 2. The results from this ECG must be available, assessed, and initialed and dated by the Investigator prior to Visit 4.
- ^l Includes Hematology and Clinical chemistry. Please refer to Table 3
- ^m Only for WOCBP. Blood sample will be collected for serum β HCG test, only if urine test is positive.
- ⁿ SAEs will be collected from the time of informed consent and AEs will be collected from the start of the placebo lead-in (Visit 2).

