8.2 Sample size estimate

The primary endpoint is the change from baseline in HbA1c at Week 24. From post-hoc results of similar clinical studies (Study MB102029, Study D1690C00018, and Study D1690C00019) when patients meeting eGFR entry criteria like those in this current study were selected, the mean placebo-corrected change from baseline in HbA1c after 24 weeks of treatment for the current study is estimated to be -0.3% for dapagliflozin 10 mg.

Assuming a common standard deviation (SD) of 0.9% in the primary endpoint, 143 patients per treatment group with both baseline and at least one post-baseline HbA1c measurement will provide 80% power to detect a treatment difference of 0.3% in the primary endpoint at a two-sided significance level =0.05, using a two-sample t-test. Assuming that 5% of randomized patients fail to qualify for inclusion in the full analysis set due to missing baseline and/or all post-randomization values for this primary endpoint, a total of 302 randomized patients (151 per treatment group) are needed for the study.

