8.5.1 Analysis of the primary variable (s)

The primary endpoint is the changes from baseline in HbA1c at Week 24. The primary analysis of the primary endpoint will be based on a mixed effects model with repeated measures (MMRM) using ‘direct likelihood’, including patients in the Full Analysis Set who have a baseline measurement and at least one post-baseline measurement. The primary analysis will only include measurements prior to the administration of rescue medication. Measurements made following rescue administration will not be included in analysis.

The SAS procedure PROC MIXED will be used for the primary analysis. The primary analysis model will include the fixed categorical effects of treatment, week, randomization stratification factor (i.e. anti-diabetic treatment strata) and treatment-by-week interaction as well as the continuous fixed covariates of baseline measurement and baseline measurement-by-week interaction. An unstructured matrix for the within-patient error variance-covariance will be used. The denominator degrees of freedom will be calculated according to the Kenward-Roger method. A number of back-up models will be defined in the statistical analysis plan in case of non-convergence of the preferred model or other issues. Point estimates and 95% confidence intervals for the mean change within each treatment group as well as the difference in mean change between the dapagliflozin and placebo will be calculated. P-value of the differences in week 24 visit estimates between dapagliflozin and placebo will be calculated.

A variety of sensitivity analyses will be specified in the Statistical Analysis Plan to assess the robustness of the primary analysis results, including a sensitivity analysis of the effect of baseline eGFR on the results obtained in primary analysis as well as sensitivity analyses which include all data pre- and post-rescue. In order to assess the robustness of the primary analysis results on the missing data assumptions, the amount of missing data, the distribution of missing data among treatment groups, and the reasons for missing data will be examined. If substantial amount of missing data is observed or if imbalance occurs amongst the treatment

groups, additional sensitivity analyses, including those based on alternative missing data assumptions, may be performed.

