## 1. STUDY DETAILS

### 1.1 Study Objectives

#### 1.1.1 Primary Objective

The primary objective is to compare the mean change from baseline in HbA1c between dapagliflozin 10 mg and placebo, after 24 weeks of oral administration of double-blind treatment in patients with type 2 diabetes who have inadequate glycemic control, defined as HbA1c  $\geq 7.0\%$  but  $\leq 11\%$  at Visit 1, and CKD stage 3A (eGFR 45 to 59 mL/min/1.73 m^2, inclusive, at Visit 1, or Visit 2, or Visit 3 and eGFR 40 to 65 mL/min/1.73 m^2, inclusive, at Visit 1).

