**Table 10 Summary of Analysis to meet primary efficacy objective of HbA1c**

Analysis type	Estimand	Missing Data Assumption	Imputation Method	Analysis set
Repeated measures mixed model of $\Delta$ HbA1c to Week 24 (prior to rescue and treatment discontinuation) a	Difference in outcome improvement at Week 24 without rescue and without treatment discontinuation.	MAR	No imputation	FAS a
Repeated measures mixed model of $\Delta$ HbA1c to Week 24 (prior to rescue and treatment discontinuation) b	Difference in outcome improvement at Week 24 without rescue and without treatment discontinuation. For PP analysis set only.	MAR	No imputation	PP b
Repeated Measures mixed model of $\Delta$ HbA1c to Week 24 with adjustment for baseline eGFR in addition to adjustment for baseline HbA1c (prior to rescue and treatment discontinuation)	Difference in outcome improvement at Week 24 without rescue and without treatment discontinuation.	MAR	No imputation	FAS
ANCOVA of $\Delta$ HbA1c to Week 24 from MI-RD imputation	Difference in outcome improvement at Week 24 regardless of rescue or treatment discontinuation.	MNAR	Observed and Imputed values	RAND
ANCOVA of $\Delta$ HbA1c to Week 24 from washout imputation	Difference in outcome improvement at Week 24 regardless of rescue or treatment discontinuation.	MNAR	Observed and Imputed values	RAND

$\Delta$ HbA1c=change from baseline in HbA1c; PP=Per Protocol; FAS = Full analysis set

a The primary analysis

b The sensitivity analysis on PP will be applied to primary efficacy endpoint only if there will be more than 10% difference in number of patients from FAS

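### Does the baseline-eGFR sensitivity analysis fall short because it cannot show whether the treatment effect changes with eGFR?

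*SAP*

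**What the plan says.** Protocol 8.5.1 lists, among the analyses meant to test how robust the primary result is, "including a sensitivity analysis of the effect of baseline eGFR on the results obtained in primary analysis". The protocol's version history, in its entry on Section 8.5.1, says this will be done by adding a single baseline-eGFR term to the primary model.

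SAP 4.2.6.2 carries this out in the Full Analysis Set, "with adjustment for baseline eGFR and baseline eGFR-by-week interaction, in addition to adjustment for baseline HbA1c and baseline HbA1c-by-week interaction". The model it extends, in SAP 4.1.6.1, has treatment, week, stratum, treatment-by-week, baseline and baseline-by-week; treatment interacts only with week. SAP Table 10 describes the row as a repeated-measures model "with adjustment for baseline eGFR in addition to adjustment for baseline HbA1c (prior to rescue and treatment discontinuation", and gives it the same estimand as the primary analysis.

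For the primary model, SAP 4.2.6.1 adds a Baseline*Week*Treatment term as a model check, looking for a "treatment effect across visits which differs in dependency on baseline values". The baseline there is HbA1c.

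Treatment-by-subgroup questions are handled elsewhere. Protocol 8.5.3 lists subgroups and ends with an open entry for others. Protocol 8.5.6 and SAP section 4 provide for interaction terms in exploratory subgroup analyses. SAP Table 14 gives an example of a subgroup-by-treatment contrast. The text of SAP 4.2.6.6 and the contents of Table 15 are redacted.

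**The concern.** Protocol 1.1 says the drug's "ability to inhibit renal glucose reabsorption declines with decreasing eGFR", so a treatment effect that depends on eGFR is plausible here. The entry rule is also loose relative to the analysis baseline. The 45-59 range must be met only once, "inclusive, at Visit 1, or Visit 2, or Visit 3 and eGFR 40 to 65" at Visit 1, whereas "Lab values from Visit 4 will be used as baseline values for study entry". Baseline eGFR can therefore lie outside 45-59, and SAP Table 9 has categories below 45 and from 60 upward.

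Against that background, an analysis described as looking at the effect of baseline eGFR invites the reader to expect an answer on effect modification. A common-slope model cannot give one. The SAP checks treatment-by-baseline dependence for HbA1c and states no counterpart for eGFR, which makes the omission look like an oversight. At stake would be a false reassurance: an unchanged estimate of about -0.30 read as proof that the effect is the same at eGFR 45 and at 59.

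**Working it through.** **Inputs.** From Protocol 8.2: SD 0.9, 143 evaluable patients per arm (N = 286), difference 0.3, 5% loss. Assumed, because the documents give no values: SD of baseline eGFR 4 to 10 mL/min/1.73 m², and a linear gradient g in the treatment effect (% HbA1c per mL/min/1.73 m²).

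**1. The plan's own figure.** Protocol 8.2 claims "80% power to detect a treatment difference of 0.3% in the primary endpoint at a two-sided significance level =0.05, using a two-sample t-test". The normal formula gives 2 × (1.960 + 0.842)² × (0.9/0.3)² = 141.3, so 142 per arm. The exact t-test gives 142.2, so 143, with power 0.802. Then 143/0.95 = 150.5, so 151 per arm and 302 in total. The figure reproduces and the concern does not touch it.

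**2. What the planned row estimates.** Let the effect at eGFR x be d(x) = -0.30 - g(x - 52), where 52 is the midpoint of 45 and 59. With eGFR independent of arm by randomization, a common-slope model estimates the average of d(x), whatever g is. Week 24 linear-model simulation (286 patients, eGFR SD 5, 2000 runs per row):

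| g | True effect at 45 / 59 | Primary model | eGFR-adjusted | Interaction test rejects |
|---|---|---|---|---|
| 0 | -0.30 / -0.30 | -0.296 | -0.295 | 5% |
| 0.02 | -0.16 / -0.44 | -0.299 | -0.299 | 16% |
| 0.04 | -0.02 / -0.58 | -0.298 | -0.298 | 46% |
| 0.06 | +0.12 / -0.72 | -0.304 | -0.304 | 80% |

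The structural statement is therefore true: this row says nothing about the gradient.

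**3. Whether it was meant to.** Three statements of purpose agree. Protocol 8.5.1 asks about the influence of eGFR on the primary result. The version history specifies one added term. SAP Table 10 calls the row adjustment and keeps the primary estimand. The SAP delivers that and lets the eGFR slope vary by week as well. The row has a job: under Protocol 3.5 randomization is stratified by background therapy only, so nothing in the design balances eGFR, and adjustment handles chance imbalance.

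**4. Whether the HbA1c check creates a duty for eGFR.** The three-way term in SAP 4.2.6.1 tests an assumption about a covariate already in the primary model. eGFR is not in that model. The SAP also plans no effect estimates at chosen HbA1c values, so there is no existing eGFR-type output to mirror.

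**5. What interaction terms would give.** The standard error of the slope difference is 2 × 0.9/(SD_eGFR × √286), and the detectable slope at 80% power is 2.802 times that.

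| SD of eGFR | SE | Detectable slope | Change over 45-59 (×14) | Power at g = 0.02 |
|---|---|---|---|---|
| 4 | 0.027 | 0.075 | 1.04 | 12% |
| 5 | 0.021 | 0.060 | 0.83 | 16% |
| 8 | 0.013 | 0.037 | 0.52 | 32% |
| 10 | 0.011 | 0.030 | 0.42 | 47% |

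For scale, a uniform spread over the Visit 1 range 40-65 has SD 25/√12 = 7.2.

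The half-width at eGFR 45 or 59 is 1.96 × √(0.1064² + (7 × SE)²), where 0.1064 = 0.9 × √(2/143). For SD 5 it is 1.96 × √(0.0113 + 0.0222) = 0.36; for SD 8, 1.96 × √(0.0113 + 0.0087) = 0.28. Overall it is 1.96 × 0.1064 = 0.21. A separate simulation that applied the entry rule (true eGFR uniform on 40-65, within-patient CV 7%, g = 0.02) gave -0.148 ± 0.305 at 45, or -0.45 to +0.16, and -0.434 ± 0.287 at 59, or -0.72 to -0.15. Both intervals contain -0.30. Restricting to Visit 4 eGFR of 45 to below 60 gave -0.288 ± 0.254, close to the overall effect.

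**The case for a change.** The strongest case for the concern is that the row is close to uninformative: under randomization it will nearly always agree with the primary analysis, even if the effect reverses sign within the eligible range. The amendment that relaxed the eGFR criterion also introduced this analysis, so the natural question is whether patients at the edges respond differently. In simulations under assumed eGFR distributions, 13-38% of patients have a Visit 4 value outside 45 to below 60. The remedy is cheap, and estimates with confidence intervals do not need a well-powered test.

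The algebra stands, and so does the warning about interpretation. The rest does not make a flaw. Agreement with the primary analysis is what a robustness check is expected to show, and no covariate adjustment of this form can reveal an interaction. No section says that an unchanged estimate will be taken as constancy across eGFR. The gradient of 0.02 is an assumption: Protocol 1.1 gives urinary glucose excretion about 50% lower in CKD stage 3 than with normal or mildly impaired function, but no HbA1c slope within 45-59. Much of the spread in Visit 4 eGFR is measurement noise: in the two wider scenarios 39-50% of the out-of-range patients have a true value in range, and in the narrowest all do. If the gradient follows true eGFR, the contrast seen on Visit 4 values shrinks to about -0.18 to -0.22 at 45 against -0.38 to -0.41 at 59.

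**Conclusion.** The concern does not hold. The named analysis contains no treatment-by-eGFR term, but it was specified as covariate adjustment and does that. No stated number, rule or protocol requirement is contradicted. The place for effect modification is the subgroup plan. Its eGFR content, if any, is hidden by redaction, so it can be neither asserted nor called missing.

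The extra terms would be an optional exploratory estimate of low yield. At a gradient of 0.02 the interaction test has 12-32% power for an eGFR SD of 4 to 8, rising to 47% at an SD of 10, and in the worked example the intervals at both ends of the range still include the overall -0.30.

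The reading of the model terms rests on the text alone. The sizes rest on an assumed linear gradient, an assumed eGFR spread and Week 24 linear models in place of the full repeated-measures model; the common-slope argument is the same in both. When results are reported, this row should be described as adjustment for eGFR and not as evidence of a constant effect.
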